14.1 Quality Management: Critical Processes and Data

The following processes and data have been identified during the risk management activities for this trial as critical to ensure human subject protection and the reliability of trial results.

The Sponsor and its designees will ensure a close oversight of the site's activities related to the trial. Throughout the study, the clinical study team will work to ensure that the trial is operationally feasible and focuses on study activities essential to human subject protection and the reliability of trial results, including (but not limited to):

- Study protocol design and implementation
- Tools and procedures supporting data collection and processing

- Tools and procedures safeguarding the rights and protection of human subjects
- Activities essential to trial decision-making and compliance

15. REPORTING AND RECORDING OF DATA

All required study data must be entered in the eCRF created for the study. Training on the system will be provided to all sites, including instructions on how to address missing data, corrections, query procedures and electronic signatures. Only individuals who are identified on the authorised signature page may enter/correct data in the eCRF. For those subjects who withdraw before completion of the study, all available efficacy and safety data must be entered in the eCRF. Incomplete or inconsistent data on the eCRF will result in data queries addressed to the Investigator for resolution.

15.1.1 Source Documentation

The Investigator must maintain adequate and accurate source documents upon which case reports for each subject are based. They are to be separate and distinct from eCRFs. These records should include detailed notes on:

- The medical history
- The basic identifying information, such as demographics, that link the subject's source documents with the eCRFs
- The results of all diagnostic tests performed, diagnoses made, therapy provided and any other data on the condition of the subject
- The subject's exposure to study treatment
- All AEs and pregnancies
- All special situations as defined in Section 10.8.1
- The subject's exposure to any concomitant therapy (including date and quantity dispensed)
- All relevant observations and data on the condition of the subject throughout the study
- The oral and written communication with the subject regarding the study treatment (including the risks and benefits of the study). The date of informed consent must be recorded in the source documentation

All data for the study must be available in source documentation.

15.1.2 Records Retention

The Investigator must arrange for the retention of all study documentation (such as eCRF files or printed forms, research files, and master files) for the duration specified in their respective site contract or as specified by the applicable Regulatory Authority, whichever is longer. The Sponsor will inform the Investigator in writing when files can be destroyed.

Archived data may be held on DVD, USB or through a secure file transfer protocol site, or electronic record, provided that a back-up copy exists and that a hard copy can be generated if required.

The Investigator must inform the Sponsor immediately if any documents are lost, to be transferred to a different facility, or to be transferred to a different owner.

15.1.3 Site Documentation

The Investigator must maintain adequate and accurate records to enable the conduct of the study to be fully documented and the study data to be subsequently verified.

16. PROCEDURE FOR MODIFICATION OF PROTOCOL OR PREMATURE TERMINATION OF THE STUDY

16.1 Protocol Deviations

The Investigator will not deviate from the protocol without prior written approval from the Sponsor, except in medical emergencies. In the event of a medical emergency, the Investigator must notify the Sponsor Medical Expert as soon as possible. Any other change to the protocol must be implemented as an amendment to the protocol (see Section 16.2). The criteria describing protocol deviation(s) and how they will be handled will be documented in the SAP.

16.2 Protocol Amendments

Protocol amendments, except where necessary to eliminate an immediate hazard to subjects, must be made only with the prior approval of the Sponsor. Each applicable Regulatory Authority/IEC will review and approve amendments prior to their implementation. Regulatory Authority/IEC approval need not be obtained prior to removal of an immediate hazard to subjects.

16.3 Study Termination

The Sponsor reserves the right to terminate the study in its entirety or at a site at any time. Reasons for termination may include (but are not limited to) unsatisfactory subject enrolment with respect to quality and/or quantity, site is unable to comply with the requirements of the protocol or GCP, or data recording is inaccurate and/or incomplete.

In terminating the study, the Sponsor and the Investigator will assure that adequate consideration is given to the protection of the subject's interests. Both parties will arrange the procedures on an individual basis after review and consultation and in accordance with the study contract.

17. POLICY FOR PUBLICATION AND PRESENTATION OF DATA

The Sponsor is committed to the timely communication of data from clinical research trials, following the Pharmaceutical Research and Manufacturers of America principles [23]. The Clinical Trial Agreement describes the Sponsor's publication terms.

Where possible, authorship will be agreed at the beginning of the study. The authors will form a publication committee and this committee will propose and develop appropriate scientific manuscripts or abstracts from the study data. Investigators may not present or publish partial or complete study results individually. Any manuscript or abstract proposed by the Investigators must be reviewed and approved in writing by Vifor Fresenius Medical Care Renal Pharma Ltd. before submission for publication. Names of all Investigators participating in the study will be included in the publication.

The publication committee for a study will comprise of authors selected in adherence with the International Committee of Medical Journal Editors criteria for authorship [24]. That is, all authors must meet each of the following 4 criteria:

1. Substantial contribution to the conception and design of the work; or the acquisition, analysis, or interpretation of data for the work; and
2. Drafting the work or revising it critically for important intellectual content; and
3. Final approved of the version to be published; and
4. Agreement to be accountable for all aspects of the work in ensuring that questions related to the accuracy or integrity of any part of the work are appropriately investigated and resolved.

In addition, certain Sponsor employees involved in the design and conception of the protocol, study management and data analysis and interpretation are qualified authors and will be included in the publication committee e.g., the lead physician, statistician and study project manager or their equivalents.

Appendix 1 Worst Itching Intensity-Numerical Rating Scale

WORST ITCHING INTENSITY NUMERICAL RATING SCALE (NRS)

**SUBJECT
NUMBER:** -

Completed in Dialysis Unit or at Home? (please mark only one)

[figure not shown]
- Dialysis Unit
- Home

INSTRUCTIONS

Please indicate the intensity of the **WORST ITCHING** you experienced over the past 24 hours by marking the box with the number that best describes it. After completing the scale below, please provide your initials in the **SUBJECT INITIALS** box indicating that you completed the scale by yourself and the **DATE** and **TIME** you completed the scale.

Worst Itching Over the Past 24 Hours

Please indicate the intensity of the **WORST ITCHING** you experienced over the past 24 hours.

Date Completed:								Time:			SUBJECT INITIALS				
						2	0				AM	PM	First	Middle	Last
D	D	M	M	M	Y	Y	Y	Y							

Note: Section to be completed by the site staff after form has been collected from subject

STUDY DAY NUMBER:

11

Time:

□ □ : □ □
□ AM □ PM

SUBJECT INITIALS		
First	Middle	Last

Appendix 2 New York Heart Association Classification of Heart Failure

Class	Patient Symptoms
I	No limitation of physical activity. Ordinary physical activity does not cause undue fatigue, palpitation, dyspnea (shortness of breath).
II	Slight limitation of physical activity. Comfortable at rest. Ordinary physical activity results in fatigue, palpitation, dyspnea (shortness of breath).
III	Marked limitation of physical activity. Comfortable at rest. Less than ordinary activity causes fatigue, palpitation, or dyspnea.
IV	Unable to carry on any physical activity without discomfort. Symptoms of heart failure at rest. If any physical activity is undertaken, discomfort increases.

Appendix 3 Skindex-10 Scale

SKINDEX-10 QUESTIONNAIRE

SUBJECT
NUMBER:

 -

INSTRUCTIONS: During the past **WEEK**, how often have you been bothered by:

	0 (Never bothered)	1	2	3	4	5	6 (Always bothered)
1. Your itching							
2. The persistence/reoccurrence of your itching							
3. The appearance of your skin from scratching							
4. Frustration about your itching							
5. Being annoyed about your itching							
6. Feeling depressed about your itching							
7. Feeling embarrassed about your itching							
8. The effects of your itching on your interactions with others (for example: interactions with family, friends, close relationships, etc.)							
9. The effects of your itching on your desire to be with people							
10. The effect of your itching making it hard to work or do what you enjoy							

Date Completed:

2	0		
Y	Y	Y	Y

D D M M M

Time:

AM PM

SUBJECT INITIALS

First Middle Last

Note: Section to be completed by the site staff after form has been collected from subject

STUDY DAY NUMBER:

Site Staff Initials:

Appendix 4 5-D Itch Scale

1.	DURATION:	During the last 2 weeks, how many hours a day have you been itching?						
		Less than 6 hrs/day	6-12 hrs/day	12-18 hrs/day	18-23 hrs/day	All day		
								
2.	DEGREE:	Please rate the intensity of your itching over the past 2 weeks						
		Not present	Mild	Moderate	Severe	Unbearable		
								
3.	DIRECTION:	Over the past 2 weeks has your itching gotten better or worse compared to the previous month?						
		Completely resolved	Much better, but still present	Little bit better, but still present	Unchanged	Getting Worse		
								
4.	DISABILITY:	Rate the impact of your itching on the following activities over the last 2 weeks						
		Sleep	Never affects sleep	Occasionally delays falling asleep	Frequently delays falling asleep	Delays falling asleep and occasionally wakes me up at night	Delays falling asleep and frequently wakes me up at night	
								
		Leisure/Social	N/A	Never affects this activity	Rarely affects this activity	Occasionally affects this activity	Frequently affects this activity	Always affects this activity
								
		Housework/ Errands						
								
Work/School								

5. DISTRIBUTION:	Mark whether itching has been present in the following parts of your body over the last 2 weeks. If a body part is not listed, choose the one that is closest anatomically.			
	Head/Scalp		Soles	
	Face		Palms	
	Chest		Tops of Hands/Fingers	
	Abdomen		Forearms	
	Back		Upper Arms	
	Buttocks		Points of Contact w/ Clothing (e.g., waistband, undergarment)	
	Thighs			
	Lower legs		Groin	
	Tops of Feet/Toes			

Appendix 5 Patient Global Impression Change

Since the start of the study, my overall status is:

✓ *one box only:*

- [1] Very Much Improved
- [2] Much Improved
- [3] Minimally Improved
- [4] No Change
- [5] Minimally Worse
- [6] Much Worse
- [7] Very Much Worse

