3.4 Secondary Efficacy Endpoints

- Proportion of subjects achieving ≥ 3 -point improvement from baseline with respect to the weekly mean of the daily 24-hour WI-NRS at Week 4 of the double-blind period.
- Proportion of subjects achieving ≥ 3 -point improvement from baseline with respect to the weekly mean of the daily 24-hour WI-NRS at Week 8 of the double-blind period.
- Proportion of subjects achieving ≥ 3 -point improvement from baseline with respect to the weekly mean of the daily 24-hour WI-NRS at Week 12 of the double-blind period.
- Proportion of subjects achieving ≥ 4 -point improvement from baseline with respect to the weekly mean of the daily 24-hour WI-NRS at Week 4 of the double-blind period.
- Proportion of subjects achieving ≥ 4 -point improvement from baseline with respect to the weekly mean of the daily 24-hour WI-NRS at Week 8 of the double-blind period.
- Proportion of subjects achieving ≥ 4 -point improvement from baseline with respect to the weekly mean of the daily 24-hour WI-NRS at Week 12 of the double-blind period.
- Change from baseline in itch-related QoL at the end of Week 12 of the double-blind period, as assessed by the 5-D itch scale total score.
- Change from baseline in itch-related QoL at the end of Week 12 of the double-blind period, as assessed by the Skindex-10 scale total score.

- Change from baseline in the weekly mean of the 24-hour WI-NRS score at each week of the double-blind period.
- Change from baseline in itch-related QoL at each time point of the double-blind period and open-label extension phase, as assessed by the 5-D itch scale total score.
- Change from baseline in itch-related QoL at each time point of the double-blind period and open-label extension phase, as assessed by the Skindex-10 scale total score.
- Patient Global Impression of Change.

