9.7 PRO Measures

The effect of difelikefalin on itch will be measured by means of the following PRO measures:

- WI-NRS score
- Skindex-10 scale
- 5-D itch scale

Patient Global Impression of Change Subjects will be trained on completion of the WI-NRS scale before the first visit of the run-in period and will be trained on the other itch-related PRO measures at any time before Day 1 of the double-blind period. All questionnaires must be completed in strict adherence to the training manual for patient reported assessments.

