9.7.4 Patient Global Impression of Change

The Patient Global Impression of Change is a global PRO measure that assesses the change in itch (no change, improvement or worsening) overall relative to the start of the study [\[20\]](#). The scale has only 1 item, and the subject is asked to mark the category that best describes the change in itch ranging from “Very Much Improved” to “Very Much Worse” ([Appendix 5](#)).

10. EVALUATION, RECORDING, AND REPORTING OF AEs

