analysed using the same approach as described above fitted for the change from baseline in itch-related QoL at end of Week 12 of the double-blind period, as assessed by the 5-D itch scale total score. Repeated measures will include all values collected during each period separately.

Change from baseline in itch-related QoL at each time point of the double-blind period and of the open-label extension period, as assessed by the 5-D itch scale total score will be analysed separately using the same approach as described above fitted for the change from baseline in itch-related QoL at end of Week 12 of the double-blind period, as assessed by the 5-D itch scale total score. Repeated measures will include all values collected during each period separately.

The number and percentage of subjects for each response of the Patient Global Impression of Change will be reported as well as the count of subjects with missing values. The number and percentage of subjects who rate their itch condition as “Very much improved” or “Much Improved” at the end of Week 12 of the double-blind period/end of double-blind will be reported together. The Mantel-Haenszel estimate, adjusting for the randomisation stratification variables, of common odds ratio with its 2-sided 95% CI will be reported. Additionally, the 2-sided exact Clopper Pearson 95% CI for the proportion of subjects who rate their itch condition as “Very much improved” or “Much Improved” will be presented.

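### The Patient Global Impression of Change form asks about overall status, but the protocol describes and plans to report it as change in itch

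*Protocol*

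**What the plan says.** The Patient Global Impression of Change (PGIC) is a secondary efficacy endpoint, listed in Protocol section 3.4 by name alone: "Patient Global Impression of Change". It is completed once, at Day 85 or early termination (section 8.5).

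Section 9.7 introduces the patient-reported measures with the sentence "The effect of difelikefalin on itch will be measured by means of the following PRO measures", and the PGIC closes that list. Section 9.7.4 calls it a "global PRO measure that assesses the change in itch (no change, improvement or worsening) overall relative to the start of the study". It adds that "the subject is asked to mark the category that best describes the change in itch", and refers to Appendix 5 for the form.

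The stem in Appendix 5 reads "Since the start of the study, my overall status is". Seven options follow, from very much improved to very much worse.

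Section 12.8.2 gives the analysis. Responses are tabulated by category with a count of missing values. The top two categories are then combined: "The number and percentage of subjects who rate their itch condition as" much or very much improved. For that proportion, "The Mantel-Haenszel estimate, adjusting for the randomisation stratification variables, of common odds ratio with its 2-sided 95% CI will be reported", together with exact Clopper-Pearson intervals.

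**The concern.** The form and the text that describes and analyses it refer to different things. A haemodialysis patient's overall status depends on itch, but also on dialysis, comorbidity and side effects of treatment. If the plan is followed literally, the report will give a proportion and an odds ratio for improved itch, taken from a question that, as printed, did not ask about itch. What is at stake is the label on one named secondary result, and so what the trial can say from it.

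**Working it through.** The point involves no figure from the plan, so the check is a comparison of texts.

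| Place in the protocol | What it refers to |
|---|---|
| Section 3.4, endpoint list | PGIC by name; no construct stated |
| Section 9.7, introduction to the measures | Effect on itch |
| Section 9.7.4, description | Change in itch since study start |
| Section 12.8.2, analysis | Itch condition in the top two categories |
| Appendix 5, the form | Overall status since study start |

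1. **What agrees.** The reference point (start of the study) and the range of the scale are the same in section 9.7.4 and on the form. Only the construct differs.

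2. **Whether this is an artefact of the extracted text.** The stem in Appendix 5 is a complete sentence, options 1 to 7 are all present, and no missing figure is flagged there. None of the options mentions itch.

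3. **Comparison with the other forms.** The worst-itch rating scale (Appendix 1), Skindex-10 (Appendix 3) and the 5-D scale (Appendix 4) all name itching in what the subject reads. An example from the 5-D is "Please rate the intensity of your itching over the past 2 weeks". The PGIC is the only one of the four that does not.

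4. **Whether the non-itch part could differ between arms.** Protocol sections 1.2.2.2 and 7.1 list events in haemodialysis subjects whose incidence was at least 1.0% greater on difelikefalin than on placebo. Diarrhoea, nausea, fall, hypotension, dizziness and vomiting are on both lists. A subject whose itch improved but who became dizzy or nauseated could truthfully mark no change in overall status. This route would tend to work against difelikefalin. Changes in dialysis or comorbidity unrelated to treatment should balance in expectation under blinded 1:1 randomisation, so they mainly add noise.

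5. **What is unaffected.** The primary endpoint is the change in weekly mean worst-itch score at Week 4. The sample size in section 12.2 is built on that endpoint alone. Relabelling the PGIC changes no model, population, alpha or number of subjects.

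6. **Whether the size can be calculated.** It cannot. The documents do not say how often overall status and itch would be rated differently, either overall or by arm.

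**The case against.** The strongest reply is that this is a wording mismatch in a minor endpoint and that material not supplied might resolve it.

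- **Training and administered form.** Subjects are trained on the PGIC worksheet at the Day 85 visit (section 8.5), and questionnaires must follow a training manual (section 9.7). Neither that manual nor the form used at the Chinese sites is available here. The 5-D and Skindex-10 are due at the same visit, so the setting may also steer subjects towards itch. This stands as a limit. A reader might infer that subjects did not answer about itch; the documents neither show that nor rule it out. They show only that the printed form does not ask it.
- **Endpoint wording.** A reader might infer that the endpoint itself claims an itch effect. It does not: section 3.4 gives only the name, and the itch wording lies in the description and the analysis text.
- **Weight of the result.** Section 12.8.2 leaves secondary tests unadjusted, warns against leaning on any single one and reads them with the primary result. It names no p-value for the PGIC. The worst-itch scale, 5-D and Skindex-10 carry the itch evidence. A reader might infer that the trial's itch conclusion is in doubt; the documents give no support for that.
- **Controlling document.** The supplied SAP covers the open-label extension, lists no PGIC output and leaves double-blind endpoints to a separate SAP (SAP sections 1 and 2.6.1, Appendix 1). That SAP may already be worded differently. The finding therefore rests on the protocol.
- **Extent.** Every response is collected under the same stem, but that is not an effect size, and it does not mean that every answer misleads.

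These points limit the finding but do not remove it. Section 9.7.4 names Appendix 5 as the instrument, and nothing supplied redirects the question to itch.

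**Conclusion.** The protocol contradicts itself on what the PGIC measures. On the form as printed, the planned proportion, odds ratio and intervals describe overall status and should not be labelled as itch. This should be corrected because it changes what may be concluded from a named secondary endpoint. It goes no further than that endpoint.

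The size of any gap between an overall-status result and an itch result is unknown. The one mechanism that the documents identify as differing between arms, adverse events, would tend to understate benefit on itch.

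The conclusion assumes that the administered form matches Appendix 5 and that the training text does not direct the answer to itch. Confidence is high for the textual mismatch, and lower for any statement about what subjects had in mind.

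**What to change.** 1. Check the administered Chinese-language form and the PGIC part of the training manual.
2. Unless they direct the answer to itch, describe and report the endpoint as *overall status much or very much improved* in Protocol sections 9.7, 9.7.4 and 12.8.2. Use the same wording in the double-blind SAP and its outputs, and do not present the result as itch-specific.
3. If they do direct the answer to itch, keep the itch label, cite that text in section 9.7.4 and correct Appendix 5 to match what was used.
4. Reword the item to ask about itch only if collection on the form has not begun. The SAP revision history records an update after a first dry run, dated 23 October 2024, so this option has probably passed.

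The cost is a document check and edits to text and output titles. No new data, model change or loss of power is involved.

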SOC	System organ class
TFL	Tables, figures and listings
WI-NRS	Worst Itching Intensity Numerical Rating Scale

SAP REVISION HISTORY

Version	Effective Date	Summary of Changes
0.1	21Jun2024	Initial version, based on protocol V 2.0, 29-Mar-2022
0.2	24July2024	Updated according to sponsor's comments
0.3	07Aug2024	Updated according to sponsor's comments
1.0	12Aug2024	Version 1.0 finalised
1.1	23Oct2024	Updated according to dry run 1 comments
2.0	27Nov2024	Version 2.0 finalised

